### Adverse Event Severity

Adverse events are to be graded according to the categories detailed below:

Mild:	Mild; asymptomatic or mild symptoms; clinical or diagnostic observations only; intervention not indicated.
Moderate:	Moderate; minimal, local or noninvasive intervention indicated; limiting age appropriate instrumental activities of daily living (eg, preparing meals, shopping for groceries or clothes, using the telephone, managing money).
Severe:	Severe or medically significant but not immediately life-threatening; hospitalization or prolongation of hospitalization indicated; disabling; limiting self-care activities of daily living (ie, bathing, dressing and undressing, feeding self, using the toilet, taking medications, and not bedridden); OR life-threatening consequences; urgent intervention indicated; OR death related to an adverse event.

Changes in severity should be documented in the medical record to allow assessment of the duration of the event at each level of severity. Adverse events characterized as intermittent require documentation of the start and stop of each incidence. When changes in the severity of an AE occur more frequently than once a day, the maximum severity for the experience that day should be noted. If the severity category changes over a number of days, then those changes should be recorded separately (with distinct onset dates).

Adverse event severity and seriousness are assessed independently. ‘Severity’ characterizes the intensity of an AE. ‘Serious’ is a regulatory definition and serves as a guide to the Sponsor for defining regulatory reporting obligations (see definition for SAE).

### **Relationship of the Adverse Event to Study Treatment**

The relationship of each AE to study drug should be evaluated by the Investigator by a “yes” or “no” response to the question: “Is there a reasonable possibility that the event may have been caused by the study drug?” A “yes” response indicates that the event is considered as related to the study drug.

The relationship of each AE to the protocol-specified background antihypertensive medication should also be assessed by the Investigator.

#### **6.5.6.2. Eliciting and Recording Adverse Events**

##### **Eliciting Adverse Events**

The patient and legal guardian, if applicable, should be asked about medically relevant changes in the patient’s health since the last visit. The patient and legal guardian, if applicable, should also be asked if the patient has been hospitalized, had any accidents, used any new medications, or changed concomitant medication routines (both prescription and over-the-counter). In addition to patient observations, AEs will be documented from any clinically relevant laboratory findings, physical examination findings, ECG changes, or other findings that are relevant to patient safety.

##### **Recording Adverse Events**

The Investigator is responsible for recording non-serious AEs that are observed or reported by the patient after administration of the first dose of study treatment during the Run-in period regardless of their relationship to the study treatment through the end of study. Study treatment is defined as protocol-specified background antihypertensive medication or study drug (zilebesiran or placebo). Non-serious AEs will be followed until the end of study. Events occurring after signing of the ICF and before the Run-in period will be captured as medical history (see Section 6.1), while AEs that occur after study treatment, and baseline events that worsen after study treatment, must be recorded as AEs.

The Investigator is responsible for recording SAEs that are observed or reported by the patient after the time when the informed consent is signed regardless of their relationship to study treatment through the end of study. SAEs will be followed until satisfactory resolution, until baseline level is reached, or until the SAE is considered by the Investigator to be chronic or the patient is stable, as appropriate.

All AEs must be recorded in the source records for the clinical study center and in the eCRF for the patient, whether or not they are considered to be related. Each AE must be described in

detail: onset time and date, description of event, severity, relationship to study treatment, action taken, and outcome (including time and date of resolution, if applicable).

For SAEs, record the event(s) in the eCRF and, as applicable, the SAE form.

For AEs that are considered AEs of clinical interest (Section 6.5.6.1), the supplemental AEs of Clinical Interest eCRF should be completed. Additional clinical and laboratory information may be collected. Refer to eCRF completion guidelines for details on reporting events in the supplemental AEs of Clinical Interest eCRF.

For all ISRs, the Investigator, or delegate, should submit an Injection Site Reaction Signs or Symptoms eCRF, recording additional information regarding each injection site reaction that is entered on the AE eCRF (eg, symptom[s], injection site location, follow-up actions taken).

#### **6.5.6.3. Reporting Adverse Events of Clinical Interest to Sponsor/Designee**

For AEs that are considered AEs of clinical interest (Section 6.5.6.1), the Sponsor or its designee should be notified within 24 hours using the appropriate eCRF.

#### **6.5.6.4. Serious Adverse Events Require Immediate Reporting to Sponsor/Designee**

An assessment of the seriousness of each AE will be made by the Investigator. Any AE and laboratory abnormality that meets the SAE criteria in Section 6.5.6.1 must be reported to the Sponsor or designee within 24 hours from the time that clinical study center staff first learns of the event. All SAEs must be reported regardless of the relationship to study treatment.

The initial report should include at least the following information:

- Patient's study number
- Description and date of onset of the event
- Criterion for serious
- Preliminary assignment of relationship to study treatment, and
- Investigator/site information

To report the SAE, complete the eCRF and, as applicable, the SAE form. Within 24 hours of receipt of follow-up information, the Investigator must update the eCRF and, as applicable, the SAE form. SAEs must be reported using the contact information provided in the Study Manual.

Appropriate remedial measures should be taken by the Investigator using the Investigator's best medical judgment to treat the SAE. These measures and the patient's response to these measures should be recorded. All SAEs, regardless of relationship to study treatment, will be followed by the Investigator until satisfactory resolution or the Investigator deems the SAE to be chronic or stable. Clinical, laboratory, and diagnostic measures should be employed by the Investigator as needed to adequately determine the etiology of the event.

#### **6.5.6.5. Sponsor Safety Reporting to Regulatory Authorities**

The Sponsor or its representative will report certain study events in an expedited manner to the Food and Drug Administration, the European Medicines Agency's EudraVigilance electronic

system according to Directive 2001/20/EC, and to all country Regulatory Authorities where the study is being conducted, according to local applicable regulations.

#### **6.5.6.6. Serious Adverse Event Notification to the Institutional Review Board/Independent Ethics Committee**

Suspected unexpected serious adverse reactions will be reported to the IRB/IEC per their institutional policy by the Investigator or Sponsor (or Sponsor designee) according to country requirements. Copies of each report and documentation of IRB/IEC notification and acknowledgement of receipt will be kept in the Investigator's study file.

#### **6.5.6.7. Pregnancy Reporting**

If a female patient becomes pregnant during the study through safety follow-up (see Section 3.1), the Investigator must report the pregnancy to the Sponsor or designee within 24 hours of being notified of the pregnancy. Details of the pregnancy will be recorded on the pregnancy reporting form. The patient should receive any necessary counseling regarding the risks of continuing the pregnancy, the possible effects on the fetus, and be counseled to not breastfeed for 90 days after the last dose of study drug.

The pregnancy should be followed by the Investigator until completion. At the completion of the pregnancy, the Investigator will document the outcome of the pregnancy. If the outcome of the pregnancy results in a postpartum complication, spontaneous abortion, stillbirth, neonatal death, or congenital anomaly, then the Investigator should follow the procedures for reporting an SAE as outlined in Section 6.5.6.4.

#### **6.5.6.8. Reporting of Overdose and Other Special Situations**

An overdose is defined as any dose of study drug administered to the participant or taken by the participant that is  $>2\times$  the assigned dose during a single administration and/or  $\geq 2$  doses within  $\frac{1}{2}$  the intended dosing interval.

The Sponsor does not recommend specific treatment for an overdose.

In an event of an overdose or other special situations (eg, medication error, abuse, misuse, or CPC associated with an AE), the Investigator should:

- Contact the Medical Monitor and Sponsor within 24 hours using the contact information in the Pharmacy Manual
- Closely monitor the participant for any AE/SAE and laboratory abnormalities
- Document the amount of study drug given

Signs, symptoms, or the clinical sequelae of a suspected overdose of either study intervention or a concomitant medication will be considered AEs/SAEs.

Full details of reporting instructions for overdose and other special situations will be outlined in the Pharmacy Manual.

## 6.6. Biomarkers, DNA Genotyping, and Biospecimen Repository

Alnylam's RNAi therapeutics platform permits the highly specific targeting of investigational therapies based on genetic sequence. It is possible that variations in the target genetic sequence will result in variations in drug effect. More generally, genetic variations may account for the well-described heterogeneous manifestations of disease in patients with hypertension, as well as their responses to treatment.

Where allowed per local regulations, ethics committee (IRB/IEC) approval, and patient consent, samples will be collected as part of this study to permit exploratory investigations and the application of novel approaches to bioanalyses that may further elucidate the outcomes of this study, or potentially advance understanding of the safety, mechanism of action, and/or efficacy of zilebesiran.

Biological specimens will be collected at the intervals indicated in the Schedule of Assessments ([Table 1](#)). These specimens will be analyzed at a central laboratory. Potential exploratory investigations may include DNA, RNA, or biochemical metabolite assessments as they relate to disease progression, efficacy, or safety.

The biospecimen repository will also include residual material from routine samples (safety laboratory samples, PK samples, etc) that are obtained during the study.

These specimens will be securely stored in a central biorepository for up to 10 years following the completion of this clinical study (ie, last patient last visit), or as per local regulations. After 10 years have elapsed, samples will be destroyed.

Details regarding the collection, processing, storage, and shipping of the samples will be provided in the Laboratory Manual.

Exploratory analysis of these biospecimens will be performed by Alnylam Pharmaceuticals or its designees.

When biobanking is permitted by local regulation, study participants will be advised during the informed consent process of these biobanking details and the potential for exploratory investigation of their samples.

## 7. STATISTICS

A Statistical Analysis Plan (SAP) will be finalized before database lock and study unblinding for the analysis of the primary endpoints and secondary endpoints measured at Month 3. The plan will detail the implementation of the statistical analyses in accordance with the principal features stated in the protocol.

### 7.1. Determination of Sample Size

Approximately 630 patients will be randomized to receive either zilebesiran or placebo with sample sizes in each of the patient cohorts with protocol-specified background antihypertensive medication as follows:

- Olmesartan cohort: 300 patients
- Amlodipine cohort: 210 patients

- Indapamide cohort: 120 patients

Assuming a standard deviation of 16 mmHg in change from baseline in 24-hour mean SBP assessed by ABPM and 15% dropout rate from baseline to Month 3, with 2-sided significance level of 0.05 for each of the comparisons (zilebesiran versus placebo as add-on to olmesartan; zilebesiran versus placebo as add-on to amlodipine; zilebesiran versus placebo as add-on to indapamide), these sample sizes will provide at least 80% power to detect the following difference between zilebesiran versus placebo:

- 5 mmHg as add-on to olmesartan
- 6 mmHg as add-on to amlodipine
- 8 mmHg as add-on to indapamide

The power is assessed by simulation based on the Mixed Model with Repeated Measurements (MMRM), with change from baseline in 24-hour mean SBP assessed by ABPM at Month 3 as response variable and treatment, time, treatment-by-time as fixed factors and corresponding baseline value as a covariate.

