[Part 2 of 2 of the document. The other parts are not shown.]

The power is assessed by simulation based on the Mixed Model with Repeated Measurements (MMRM), with change from baseline in 24-hour mean SBP assessed by ABPM at Month 3 as response variable and treatment, time, treatment-by-time as fixed factors and corresponding baseline value as a covariate.

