## Statistical Methods

The planned enrollment for this study is approximately 800 patients to be randomized into the Run-in period and approximately 630 patients (300 patients in the olmesartan arm, 210 patients in the amlodipine arm, and 120 patients in the indapamide arm) to be randomized in the DB period. Randomization on Day 1 will be stratified by race (black or all other races), baseline blood pressure (24-hour mean SBP  $<$  or  $\geq$ 145 mmHg), and screening estimated glomerular filtration rate ( $<$ 60 or  $\geq$ 60 mL/min/1.73m^2).

For the primary endpoint, assuming a standard deviation of 16 mmHg in change from baseline in 24-hour mean SBP assessed by ABPM and 15% dropout rate from baseline to Month 3, with 2-sided significance level of 0.05 for each of the comparisons (zilebesiran versus placebo as add-on to olmesartan; zilebesiran versus placebo as add-on to amlodipine; zilebesiran versus placebo as add-on to indapamide), these sample sizes will provide at least 80% power to detect the following difference between zilebesiran versus placebo:

- 5 mmHg as add-on to olmesartan
- 6 mmHg as add-on to amlodipine
- 8 mmHg as add-on to indapamide

The populations (analysis sets) are defined as follows:

[figure not shown]
- **Full Analysis Set (FAS):** All randomized patients who received any amount of study drug. All by-treatment analyses based on the FAS will be grouped according to the randomized treatment arm.
- **Safety Analysis Set:** All patients who received any amount of study drug. All by-treatment analyses based on the Safety Analysis Set will be grouped according to the treatment actually received.
- **Pharmacokinetic (PK) Analysis Set:** All patients who received at least 1 full dose of zilebesiran and have at least 1 nonmissing postdose PK assessment.
- **PD Analysis Set:** All patients who received at least 1 full dose of study drug. All by-treatment analyses based on the PD Analysis Set will be grouped according to the treatment actually received.
- **All Zilebesiran Treated Set:** All patients who received any amount of zilebesiran, including patients who took zilebesiran during the 6-month DB period and patients who initially took placebo and then switched to zilebesiran after the Month 6 visit.

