#### **Patient and Disease Characteristics**

3. Has hypertension as follows:
  - a. Untreated hypertension (not taking antihypertensive medication), or
  - b. Treated hypertension on stable therapy with up to 2 antihypertensive medications. Stable therapy is defined as having no change in antihypertensive medication or dose within 30 days prior to screening.
4. Office SBP at Run-in Visit 1 as follows:
  - a.  $\geq 155$  mmHg and  $\leq 180$  mmHg for patients with untreated hypertension
  - b.  $\geq 145$  mmHg and  $\leq 180$  mmHg for patients on antihypertensive medications
5. 24-hour mean SBP  $> 130$  mmHg and  $\leq 160$  mmHg by ABPM at Run-in Visit 2 after at least 4 weeks of run-in.
6.  $\geq 80\%$  adherence to the protocol-specified background antihypertensive medication during the Run-in period as assessed by pill count performed at Run-in Visit 2.

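### The inputs printed in Section 7.1 give about 70% power per cohort, not at least 80%, and the simulation assumptions that would have to close the gap are not stated

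*Protocol*

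**What the plan says.** Section 7.1 of Amendment 1 plans three cohorts, beginning with "Olmesartan cohort: 300 patients" and followed by 210 on amlodipine and 120 on indapamide. Section 3.4 randomizes each 1:1 to zilebesiran or placebo. The assumptions are "Assuming a standard deviation of 16 mmHg in change from baseline in 24-hour mean SBP assessed by ABPM" and a "15% dropout rate from baseline to Month 3", "with 2-sided significance level of 0.05 for each of the comparisons". On that basis the protocol states that "these sample sizes will provide at least 80% power to detect the following difference between zilebesiran versus placebo": 5 mmHg on olmesartan, 6 on amlodipine and 8 on indapamide. The synopsis repeats the same inputs ("assuming a standard deviation of 16 mmHg in change from baseline in 24-hour mean SBP assessed by ABPM and 15% dropout rate"), and so does the original protocol of 25 August 2021.

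On method, Amendment 1 says: "The power is assessed by simulation based on the Mixed Model with Repeated Measurements (MMRM"), with treatment, time and their interaction as factors and baseline as a covariate. The original names the MMRM but not simulation. No baseline SD, baseline-to-change correlation, between-visit correlation or dropout pattern is printed. Inclusion criterion 5 requires a 24-hour mean SBP above 130 and at most 160 mmHg "by ABPM at Run-in Visit 2 after at least 4 weeks of run-in".

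The file also holds the closing part of what appears to be a later version. Of its sample-size section only the method sentence is shown, so its figures cannot be checked.

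**The concern.** A reader who puts the printed SD, dropout, allocation and significance level into the usual two-sample formula does not get 80%, or even 78%, in any cohort. The shortfall is nearly the same in all three, so it is not rounding. Each cohort carries its own primary test. If the printed inputs are the whole story, the chance of missing a true effect of the planned size is about 30% per cohort, against the 20% at most that the text implies. The differences the trial can reliably detect are then larger than stated, which matters when a non-significant add-on result is interpreted.

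**Working it through.** **Inputs (Sections 7.1 and 3.4).** SD of change 16; 15% dropout; 1:1; two-sided 0.05; N = 300/210/120; difference d = 5/6/8 mmHg.

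**1. Power on the printed inputs.** Evaluable n per arm = 0.85 × N/2. SE = 16 × √(2/n). Power ≈ Φ(d/SE − 1.96).

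| Cohort | n per arm | SE | d/SE | Power, normal | Power, noncentral t | No dropout, normal / t |
|---|---|---|---|---|---|---|
| Olmesartan | 127.5 | 2.004 | 2.495 | 70.4% | 70.0% | 77.2% / 77.0% |
| Amlodipine | 89.25 | 2.395 | 2.505 | 70.7% | 70.2% | 77.5% / 77.2% |
| Indapamide | 51 | 3.168 | 2.525 | 71.4% | 70.6% | 78.2% / 77.5% |

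The stated figure is not reproduced, even with nobody lost.

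**2. What 80% would take on these inputs.** Evaluable n per arm = 2 × 16² × (1.960 + 0.842)²/d² = 161/112/63. That is 379/264/149 randomized after dividing by 0.85. At the planned N, the difference detectable with 80% power is 5.6/6.7/9.0 mmHg (noncentral t; the normal approximation gives 5.6/6.7/8.9).

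**3. Credit for the baseline covariate.** Residual SD = 16 × √(1 − R²), where R² is the share of the variance of change that baseline explains. With 15% lost and no recovery of information, 80% needs a residual SD of about 14.2-14.4, so R² of 19-21%.

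R² = (slope × baseline SD)²/256, with slope that of change on baseline. Baseline SD is not stated. In a 30 mmHg window it is 30/√12 = 8.66 if uniform, and about 6-8.3 for the truncated normal shapes tried (assumption). For the olmesartan cohort (R² 20.7%) the required slope is √(0.207 × 256)/8.66 = 0.84 in absolute value, or 1.0 at a baseline SD of 7.3. Change falls almost one for one with baseline, so Month 3 SBP would be nearly unrelated to the same patient's baseline SBP.

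**4. Credit for earlier visits of dropouts.** With two visits and monotone dropout, the variance per arm is 256(1 − R²)[(1 − r²)/n₂ + r²/n₁]. Here n₂ is the number of completers, n₁ adds the dropouts seen once, and r is the residual between-visit correlation. All values of r and R² are assumed.

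- r = 0.7, every dropout seen once, R² = 15%: 80.3/80.6/81.2%. So R² of about 15% is enough in this favourable case, but it still needs a slope of 0.72 (baseline SD 8.66) or 0.85 (SD 7.3).
- r = 0.5-0.7, half to all dropouts seen once, R² = 3-8%: about 73-78% across the cohorts.

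**5. Significance level.** With the same inputs at one-sided 0.05 (1.645 in place of 1.960), power is 80.2/80.5/81.1%. The N formula then gives 299/208/118, against the planned 300/210/120.

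**The case against.** The strongest reply is that the protocol never claims 80% from a two-sample formula. It cites a simulation from a baseline-adjusted MMRM, which gains from the covariate and from dropouts' earlier recordings. That stands: a formula without those gains cannot refute it, and some inputs do reach 80%. For example, equal variances at baseline and Month 3 with correlation 0.5 give R² = (1 − 0.5)/2 = 25% and power of 82-83%. But with an SD of change of 16 this implies a baseline SD of 16, above the 15 mmHg maximum possible for any distribution confined to a 30 mmHg range.

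The 73-78% range also rests on assumed correlations, and it would move with others. The schedule's ABPM row is too broken in the available text to show which recordings precede Month 3, so the amount recovered is uncertain.

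Finally, the figures checked are those of Amendment 1 and the original. The later version may have changed them.

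**Conclusion.** The point holds as a mismatch between printed inputs and printed power: 70-71% against at least 80% in all three cohorts, and 77-78% before any dropout. The gap closes only if baseline explains about 15-21% of the variance of change, depending on how much the MMRM recovers from earlier visits. Under the eligibility window that is implausible, and the protocol prints nothing to support it.

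Two stronger readings are tempting. A reader might infer that the trial's true power is 70%. The documents do not support that, because the covariate and earlier visits add something and the simulation inputs are undisclosed; about 73-78% is reasonable under the assumptions shown. A reader might also infer that N was set at one-sided 0.05. The match is close in every cohort, but the text says two-sided throughout, so this is something to check and not a finding.

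**What to change.** Keep N. Rerun the simulation with a baseline SD compatible with the window above 130 and up to 160 mmHg. Print in Section 7.1 the residual SD, the baseline and between-visit correlations and the dropout pattern used. Unless the rerun supports 80%, choose one of two restatements in Section 7.1 and the synopsis:

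- give the power for 5/6/8 mmHg as about 70% on the stated inputs, or as the rerun's value; or
- keep 80% and give detectable differences of about 5.6/6.7/9.0 mmHg.

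Confirm from the sample-size records that the calculation used two-sided 0.05. Check the later version's sample-size section for the same point.

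The cost is a rerun and wording in two places, with no extra patients. The stated power or detectable differences will probably look less favourable.
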